1.1.2 E6.2 Telephone Screening Interview (TS)

Women who respond to study advertisements will be called on the telephone, provided a general overview of the study and, if interested, will complete a survey to determine potential eligibility. Potentially eligible respondents will be invited to attend a Screening Visit to determine eligibility. Participants will be asked to bring all medications, including prescription and over-the-counter preparations, to the visit.

1.1.3 E6.3 Screening Visit (SV)

At the Screening Visit, women will be informed about the details and requirements of the study, informed consent will be obtained, and assessment of eligibility will be performed. Participants will be asked to bring to the visit all prescription and non-prescription medications that they are currently taking and these will be recorded. Participants will have their vitals taken and be trained to keep a 3-day voiding diary and will be given baseline questionnaires assessing demographics, alcohol use, tobacco use, depression, medical history, mental status and cognitive function. Participants will be asked to complete the 3-day voiding diary at home and

return it at the Baseline Visit (V1). A participant who has an abnormal urine dipstick result may be rescreened one time for eligibility.

1.1.4 E6.4 Baseline Visit (BV)

After 1-2 weeks, candidates will return for a Baseline Visit. To be eligible, candidates must record having had at least 3 urgency incontinence episodes and more urgency than stress incontinence episodes on the 3-day voiding diary. The following questionnaires will be administered: California Verbal Learning Test (CVLT), Digit Span, Trails A & B, Digit Symbol Substitution Task (DSST), Pittsburgh Sleep Quality Index (PSQI), Physical Function and Mobility, OAB-questionnaire, and Instrumental Activities of Daily Living (IADL). Height, weight, and vital signs will be obtained, and changes in health and medications will be assessed. The list of inclusion and exclusion criteria will be reviewed and participant eligibility will be confirmed.

1.1.4.1 E6.4.a Randomization

A randomization scheme, in equal ratios of treatment groups using randomly permuted blocks of 2 and 4, will be generated by a statistician at the Coordinating Center and released only to the pharmacist at the UCSF Pharmacy. The statistician who generates the randomization scheme is not otherwise involved in the conduct of the study. Study medication is manufactured and identified as mirabegron, tolterodine tartrate, or identical placebo by Astellas, Inc. and sent to the UCSF Pharmacy. The pharmacist will label all blinded study drug with the appropriate randomization number and clinical trial information as specified by the FDA.

All eligibility information will be verified at the site prior to randomization. When a participant fulfills study inclusion and exclusion criteria, the next sequential randomization number will be assigned by study staff and irrevocably entered on a participant case report form and on a randomization log sheet. The study medication matching the randomization number will be distributed. Study medication labels will comply with all legal requirements.

The study Principal Investigator, personnel involved in the conduct of the trial, and participants will be blinded to treatment status. Unblinding of individual participants will be allowed only for clinically significant reasons, and will require the permission of the PI. Unless stipulated by the Executive Committee, treatment assignment codes will not be broken until after all participants have completed their final visit, trial data are edited and cleaned, and the trial data set locked.

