We propose a pilot study to assess the feasibility of enrolling ~50 community-dwelling, ambulatory women aged 65 years and older with urgency or mixed urgency predominate urinary incontinence into a randomized, controlled trial, to determine whether elderly women will adhere to an 8-week drug regimen and estimate the effect size necessary to show differences cognitive decline between Mirabegron and a standard anticholinergic therapy.

B. STUDY SYNOPSIS

Fifty community-dwelling women, ambulatory women with urgency or mixed urgency predominate urinary incontinence and at least 3 urgency incontinence episodes on a 3-day ~~screening diary, will be randomized to 8 weeks of Mirabegron (Myrbetriq) or tolterodine~~

tartrate (Detrol LA). The study will take place at the UCSF Women's Health Clinical Research Center.

C. SPECIFIC AIMS

The Specific Aims are to:

SA1: Assess the feasibility of enrolling and retaining women aged 65 years and older with urgency urinary incontinence in a randomized, controlled trial of an 8-week medication study.

SA2: To estimate preliminary differences in the effects of mirabegron compared to a standard anticholinergic therapy on cognitive function and calculate the standard deviation for: 1) a standard cognitive function battery, and 2) global patient perception of cognitive function.

SA3: To collect preliminary data on differences in change in physical function/mobility and other adverse events associated with Mirabegron vs. a standard anticholinergic therapy, such as dry mouth, constipation, vision, and falling.

SA4: Determine the differences in patient satisfaction between Mirabegron and a standard anticholinergic therapy in the treatment of urgency urinary incontinence.

SA5: To estimate preliminary differences in the efficacy of Mirabegron compared to a standard anticholinergic therapy on reducing urinary incontinence frequency, as assessed by validated 3-day voiding diary.

D. STUDY POPULATION

D1. Inclusion Criteria

Inclusion criteria reflect patients appropriate for treatment by primary care.

- Community-dwelling, ambulatory females \geq 65 years old

- Urgency or Mixed Urgency Predominate Urinary Incontinence (subject-reported) for ≥ 3 months prior to Screening (Visit 1)
- On a 3-day voiding diary, documentation of at least 3 urgency incontinence episodes with the number of urgency incontinence episodes greater than number of stress incontinence episodes

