- Urinary retention (post-void residual urine volume >150 cc measured by bladder scan at screening).

[figure not shown]
- Use of any electrostimulation, bladder training, or pelvic floor exercises (with certified incontinence practitioners) within 4 weeks of Screening.
- Use of mirabegron or tolterodine in the past 6 months.
- Has been treated within 4 weeks prior to Screening and/or is currently being treated with:
 - Any drug treatment for OAB
 - Any drugs with significant anticholinergic and antispasmodic effects (see exception for tricyclic antidepressants below)
- Has started treatment with or changed dose of tricyclic antidepressants or estrogens within 4 weeks prior to Screening.
- Intermittent use or unstable dose of diuretics. Treatment with diuretics initiated within 4 weeks prior to baseline and/or is not on a stable dose is not permitted.
- Treatment with potent CYP3A4 inhibitors, such as clarithromycin, ketoconazole, and itraconazole within 4 weeks prior to Screening.
- Administration of medications capable of inducing hepatic enzyme metabolism or transport (e.g., barbiturates, rifampicin, carbamazepine, phenytoin, primidone, or St. John's Wort) in the past 4 weeks.
- Administration of narrow therapeutic index drugs metabolized by CYP2D6, such as thioridazine, flecainide, and propafenone.
- Previously received any investigational drug within 30 days prior to trial entry.
- Alcohol and/or any other drug abuse in the opinion of the investigator.
- Participants who, in the opinion of the Investigator, have any medical (including known history of major hematological, renal, cardiovascular, or hepatic abnormalities) or psychological condition or social circumstances that would impair their ability to participate reliably in the trial, or those who may increase the risk to themselves or others by participating.
- Participants who, in the opinion of the investigator, are not likely to complete the trial for whatever reason.

Participants must meet all inclusion and exclusion criteria to be randomized to trial treatment.

E. STUDY DESIGN

Approximately 50 women with urgency or mixed urgency predominate urinary incontinence will be randomized in a 1-to-1 ratio to either mirabegron or tolterodine tartrate for 8 weeks.

E1. Study Overview

E2. Study Medication and Placebo

E2.a Dosing Regimen

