1.7 I1. Institutional Review Board

The study protocol, informed consent form, study questionnaires and recruitment materials must be approved by the UCSF Committee on Human Research (CHR) prior to the start of the study. Protocol amendments generated during the study must be approved by the CHR prior to their implementation. The Sponsor-Institution (UCSF) and Investigator ([name]) shall be

responsible for reporting any serious adverse events associated with the use of the study drug to the ASMA (e-mail [contact] or fax to [contact]) and to the UCSF CHR.

I2. Informed Consent Form

Before individuals may participate in any screening procedures, informed consent for all phases of the trial must be obtained. The consent form will explain in lay language the goals of the study, the visits and procedures and the risks and benefits of participating. Any amendment to the protocol generated during the study that impacts participants will be reflected in a revised consent form that must be signed again by the participant.

K. SAMPLE SIZE JUSTIFICATION

Sample sizes between 24 and 50 have been recommended for feasibility/pilot studies.³²⁻³⁵ We plan to study up to 50 women with approximately 25 randomized to Mirabegron and 25 to a standard anticholinergic therapy (Detrol LA). One of the goals of this study is to estimate the standard deviation of the neuropsychologic battery scores as well as the potential effect size of Mirabegron against its comparator. These estimates will be used to develop sample size estimates for a larger clinical trial, if indicated. Thus, power analyses based on a sample size of 50 were not done for this proposal.

L. STATISTICAL CONSIDERATIONS

SA 1: We will observe the number of weeks required to enroll 50 participants into this pilot study, track the success rate of various recruitment approaches, track the numbers of women who are screened, found eligible, enrolled/randomized, and lost to follow-up, as well as those to terminate the study or discontinue study medication early, and calculate the cost of recruitment per participant.

SA 2: Analysis of covariance (ANCOVA) will be used to estimate the preliminary performance differences on and calculate the standard deviation of cognitive test scores and physical function and mobility test scores between the Mirabegron and standard anticholinergic therapy groups at week 8, controlling for baseline.

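### The protocol prints block sizes of 2 and 4: if one assignment leaks before the next woman is randomized, hers can be guessed at about 2:1, so larger, undisclosed blocks are a cheap but modest improvement

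*Combined protocol and SAP*

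**What the plan says.** Section E6.4.a (Randomization) has the scheme generated "in equal ratios of treatment groups using randomly permuted blocks of 2 and 4". Section E (Study Design) says that about 50 women "will be randomized in a 1-to-1 ratio to either mirabegron or tolterodine tartrate for 8 weeks", and section K (Sample Size Justification) says "We plan to study up to 50 women with approximately 25 randomized to Mirabegron and 25 to a standard anticholinergic therapy". No stratification factor appears anywhere. Section B (Study Synopsis) names one site: "The study will take place at the UCSF Women's Health Clinical Research Center".

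Once eligibility has been verified, "the next sequential randomization number will be assigned by study staff" and entered irrevocably. Section E6.4 places the final eligibility review at the Baseline Visit. The criteria in D2 still in force then exclude "Participants who, in the opinion of the investigator, are not likely to complete the trial for whatever reason".

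Section E6.4.a also sets out safeguards. The list comes from a statistician with no other role in the trial, only the pharmacist receives it, and the principal investigator, trial personnel and participants are blinded. It adds: "Unblinding of individual participants will be allowed only for clinically significant reasons, and will require the permission of the PI". Section E2.b names a double-dummy method, but the only placebo it describes matches tolterodine and does not look like mirabegron.

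**The concern.** Permuted blocks create dependence between neighbouring assignments, and small blocks concentrate it on the immediate neighbour. Anyone who reads the protocol knows the sizes, and with one unstratified sequence the order of enrolment is the order of the list. Concealing the list does not prevent inference from an assignment that has become known.

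Two things are at stake:

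- **Selection.** If an assignment is known before the next woman is randomized, a guess about hers could colour the judgement of whether she is likely to complete.
- **Assessment.** A guess could carry over to women randomized just before or after an unmasked woman. Their perceived-cognition and satisfaction ratings and staff-administered cognitive tests may still lie ahead. This route does not depend on when the leak occurs relative to the next enrolment.

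The pilot is meant to supply standard deviations and effect sizes for a larger trial, so an avoidable weakness in allocation is worth removing while it is free to do so.

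**Working it through.** The plan gives no predictability figure to reproduce, and no power figure either (section K: "Thus, power analyses based on a sample size of 50 were not done for this proposal"). The only related arithmetic is 50/2 = 25 per arm, which agrees with section K.

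**Inputs.** Block sizes 2 and 4, ratio 1:1 and up to 50 women come from the documents. The mix of block sizes is not stated. I assume equally likely sizes and show a range.

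**1. One assignment known, position in block unknown.** Let p_b be the share of blocks of size b and L = Σ p_b·b the mean block length. A block of size b has m_b = max(b − k, 0) pairs that lie k places apart. Each such pair is opposite with probability (b/2)/(b − 1). Pairs that straddle two blocks are opposite with probability 0.5. Hence

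P_k = [Σ p_b·m_b·(b/2)/(b − 1) + 0.5·(L − Σ p_b·m_b)] / L.

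For the next woman (k = 1) this reduces to [Σ p_b·b/2 + 0.5]/L:

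- Blocks 2 and 4: (0.5×1 + 0.5×2 + 0.5)/3 = 0.667
- Blocks 4 and 6: (0.5×2 + 0.5×3 + 0.5)/5 = 0.600
- Blocks 4, 6 and 8: (3 + 0.5)/6 = 0.583

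If blocks of 2 make up 1/3 of the blocks, the figure for 2 and 4 is (1/3 + 4/3 + 0.5)/(10/3) = 0.650. If they make up 2/3, it is (2/3 + 2/3 + 0.5)/(8/3) = 0.688.

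**2. Known block start, such as the first woman in the trial.** P = Σ p_b·(b/2)/(b − 1). For 2 and 4 this is 0.5×1 + 0.5×2/3 = 0.833 (0.778 to 0.889 over the same range).

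| Blocks | Next woman | Known block start | 2nd after | 3rd after | 4th after |
|---|---|---|---|---|---|
| 2, 4 | 0.667 | 0.833 | 0.556 | 0.528 | 0.500 |
| 4, 6 | 0.600 | 0.633 | 0.573 | 0.547 | 0.520 |
| 4, 6, 8 | 0.583 | 0.613 | 0.565 | 0.546 | 0.527 |

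Chance is 0.500 in every column. Larger blocks lower the figure for the immediate neighbour and raise it slightly for women further away.

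**3. Timing.** The schedule in section E5 first collects adverse events at the week 2 call. Accrual is not stated. At an assumed 0.5, 1 or 2 women per week, the next enrollee after that call is the 2nd, 3rd or 5th after the woman concerned. Under blocks of 2 and 4 the probability is then 0.56, 0.53 or 0.50.

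**4. All earlier assignments known, order of block sizes unknown.** This is the extreme case. The best guess was found by updating the probability of each possible number of assignments left in the current block, over 4,000 simulated lists of 50.

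| Blocks | Best guess right | Certain | Predictable at 80% or better |
|---|---|---|---|
| 2, 4 | 72.1% | 10.7% | 55.3% |
| 4, 6 | 69.1% | 5.6% | 27.2% |
| 4, 6, 8 | 67.6% | 2.4% | 23.1% |

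A separate run of 1,000 lists gave 72.0%, 69.0% and 67.7% right, and 10.6%, 5.5% and 2.3% certain.

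**5. Arm sizes at 50.** All blocks are even, so an unfinished last block holds an even number of women. Under 2 and 4, or 4 and 6, the largest difference is 2 (26 v 24). A block of 8 cut after four like assignments gives 4 (27 v 23). If accrual stops at another number, the limit is half the largest block: 2, 3 or 4.

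**The case against.** The strongest case against the point is that the plan already conceals allocation properly and that the printed sizes do little harm. Much of it stands.

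- **Predictability is limited.** A reader might infer that blocks of 2 give away the next assignment, or that no blocked scheme could be more predictable. Neither is supported. Staff do not know which block they are in, so one leak gives about 2:1 odds. With full history, fixed blocks of 2 would make 1/2 of assignments certain, and fixed blocks of 4 would make (1 + 1/3)/4 = 1/3 certain. The random mix makes about 11% certain.
- **Timing.** Dry mouth or constipation reported at week 2 says little about the next enrollee.
- **Roles.** The documents do not say that the same people judge eligibility and assign the number.
- **Analysis.** Section L analyses SA1 as counts, weeks and cost with no comparison by arm, so arm-related selection has no SA1 contrast to bias. For SA2, the ANCOVA adjusts for baseline, which partly absorbs a baseline shift in cognition.
- **The fix is small.** With full history known, best-guess accuracy hardly moves.

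Three things survive. The safeguards protect the list, not inference from a known assignment. A leak at dispensing precedes the next randomization, and section E2.b leaves room for one because it describes no placebo matching mirabegron. And the dependence runs both ways in the sequence, so a late leak still informs guesses about neighbours not yet assessed at week 8.

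**Conclusion.** The point holds in conditional form and is minor. If an assignment becomes known before the next woman is randomized, hers is predictable at about 0.67 against 0.50 by chance, or 0.83 at a known block start, while an open-ended exclusion is still available.

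A reader might go further and infer that a leak in the blind necessarily becomes selection bias. The documents do not support that: someone would also have to act on the guess, and the list is concealed and staff blinded as planned. Nor do they establish that the two arms look different in use. Section E2.a has every participant taking a tablet and a capsule, which suggests a dummy for each product, but E2.b describes only one. The size of any resulting bias cannot be derived from the documents.

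The figures assume equally likely block sizes (range shown for 2 and 4), a guesser who knows the sizes, and one sequence at one site. The timing figures also rest on assumed accrual rates. The separate benefit of not printing the sizes has not been estimated.

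**What to change.** In section E6.4.a, replace the stated sizes with a statement that assignment is 1:1 in randomly permuted blocks of varying size. Generate the list with randomly ordered blocks of 4 and 6 (or 4, 6 and 8). Record the sizes in a restricted document held only by the list-generating statistician and the pharmacist.

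Blocks of 4 and 6 achieve most of the reduction and leave the largest split at 50 women unchanged at 26 v 24. Adding blocks of 8 lowers predictability a little further and allows 27 v 23, which is of little consequence in a pilot without a power calculation. The other cost is the slight rise in predictability for women two to four places away. Before the list is generated, the change is one sentence and one setting.

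Because the gain depends on a leak, the more useful step is to make section E2.b state clearly how mirabegron is masked, so that dispensing and tablet counts do not reveal the arm.

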1.1.5 E6.5 Follow-up Visits

E6.5.a Week 2 Phone Call

At Week 2 participants will be contacted via telephone and asked if they want to stay on the current dose of medication or increase the dose at the start of Week 3. Participants will be asked if there have been any changes in their health or medications and reminded to complete the voiding diary just prior to their Week 4 clinic visit. The coordinator will administer two assessments over the phone: the Patient Perception of Cognitive Change and the Patient Perception of Bladder Condition (PPBC).

E6.5.b Week 4

At Week 4 participants will be seen at the clinic and return the voiding diary. Study medication compliance/ accountability and changes in health will be assessed. Participants will be asked if they want to stay on the current dose of medication, or increase/decrease the current dosage. Participants will be asked to bring to the visit all prescription and non-prescription medications that they are currently taking and these will be recorded. Study medication will be dispensed. The coordinator will administer two assessments: the Patient Perception of Cognitive Change and the Patient Perception of Bladder Condition (PPBC).

E6.5c Week 8 (or Early Termination)

At Week 8 participants will be seen at the clinical centers to repeat the dipstick analysis, return the voiding diary, repeat the baseline questionnaires, and the End of Study Questionnaire or Early Termination Report. Weight and vital signs will be obtained. Study medication compliance/ accountability, changes in health and medical resource use (MD visits, surgery, and medications) will be assessed. Participants will be asked to bring to the visit all prescription and non-prescription medications that they are currently taking and these will be recorded.

F. STUDY MEASURES

The clinical assessments used in this study are accurate, reliable, and relevant. Variability is possible in the participant-reported measurements, such as study participants diaries and questionnaires that depend heavily on the participant's understanding of and compliance with protocol instructions. To minimize this possibility, case report forms will be clear and easy to

use, study site staff will be fully trained to administer the instruments, and instructions will be carefully and clearly explained to study participants, both in writing and verbally.

F1. 3-day Voiding diary

The 3-day Voiding diary includes written instructions and a sample completed diary. The diary has columns for recording the frequency of voluntary voiding episodes, urinary sensation scale (1-5), and the number of incontinent episodes by type. Study participants will also note the time they go to bed each night and the time they arise each morning. This diary has been used in large clinical trials and shown to be reliable and valid.^{16,17,19} The Voiding diary will be reviewed at Baseline Visit, Week 4 and Week 8 (or Early Termination) visits.

F2. Cognitive Assessment

Standardized neuropsychologic tests will be used to assess cognitive function and change in cognitive performance. The tests were selected as validated, easy to administer tests that may be sensitive to short-term change in cognitive function and would not create undue participant or site burden in this cohort. The tests include:

- a) California Verbal Learning Test (CVLT) evaluates recall and multi-trial learning and takes approximately 40 minutes to administer. The CVLT involves the presentation of one list of 16 words taken from three categories. Following a brief delay, the participant is asked to recall the words. Memory is then tested after another 20-minute delay.
- b) Digit Span assesses attention and short-term verbal memory (2 minutes to administer).
- c) Trail Making Test Parts A & B (Trails A & B) - assess attention and visual scanning (Trails A) and executive function (Trails B; each takes 3 minutes to administer).^{20,21} These are timed, written tests with shorter test times corresponding to better attention, visual scanning, and executive function.
- d) Digit Symbol Substitution Test (DSST) assesses incidental memory, visual scanning, and motor speed (5 minutes to administer).²² This is a timed, written test requiring subjects to translate numbers into symbols using a key; higher scores indicate greater psychomotor speed, attention, and perceptual organization.
- e) Mini Mental Status Examination (MMSE) – simple cognitive function exam that screens for cognitive loss. Participant orientation, attention, calculation, recall, language and motor skills will all be assessed. ***Participants must score at least 20/30 to qualify for the study.***

